2.1 Study Rationale

Motor imagery involves envisioning motor actions without actual execution, and has been successfully used by athletes to improve athletic performance for quite some time; for reviews see

(9-12). There is some evidence that *motor imagery* can be used to improve gait, gait-related and cognitive functions in Parkinson's disease (13-15) and post stroke (16-20), but the rehabilitative potential of motor imagery in relatively healthy elderly is currently unknown.

Recent research suggests that gait engages a distributed network of brain regions including motor, basal ganglia, cerebellar and supplementary motor regions. Based on recent findings by us (21) and others (22, 23), we hypothesize that imagined gait can be used as a rehabilitative tool for improving gait in the elderly because it engages and strengthens similar neural systems as actual gait. Age-related gait decline is particularly evident in dual-task situations that demand Executive Functions (EF) and engage the prefrontal cortex (24-31). We recently developed and validated an imagined gait protocol against an actual gait protocol that involves an ecologically-valid dual-task situation (walking while talking; WWT) that predicts falls, frailty, disability and mortality in the elderly (21, 31, 32). This imagined gait protocol involves: 1) imagined Walking (iW), imagined Talking (iT) and imagined Walking While Talking (iWWT), 2) is associated with actual WWT performance, and 3) permits us to examine the underlying neural systems of gait with functional magnetic resonance imaging (fMRI). We have identified a pattern of brain regions whose activation change as a function of imagery task difficulty (iW < iT < iWWT), and is associated with actual WWT performance (21). Increases were most notably observed in cerebellar, precuneus, supplementary motor and prefrontal cortex regions. These initial findings suggest that our imagined gait protocol engages similar neural systems as actual gait and EF and command the development of this protocol into a tool for improving gait and EF in the elderly.

The first aim of this research is to establish the efficacy of this imagined gait protocol to improve gait and EF in the elderly. We propose a pilot Randomized Clinical Trial (RCT) of 48 cognitively-healthy elderly adults who will be randomly assigned to an imagined gait intervention or an Active Control (AC; non-mobility related visual imagery) condition. The imagined gait (or AC) protocol will be administered during each study visit, and over the phone three times a week for three months (15 min/session, total of 36 sessions). Each participant will complete two study visits (pre and post). Pre-post intervention changes in gait velocity (cm/s) and cognitive performance (percent of correct letters provided; (correct/error x correct) x 100) during actual W, T and WWT will be our primary outcome measures. Age, Sex and Education will be covariates in all analyses. Other variables/covariates will be recorded (e.g. medical illnesses and history of falls), and carefully examined for potential inclusion as covariates in upcoming full-scale RCT.

The second aim is to determine neuroplasticity changes in response to our imagined gait intervention. To this end, participants will complete the imagined gait protocol (iW, iT and iWWT) during fMRI scanning at the pre and post-intervention study visits. We predict that our imagined gait protocol engages neural systems linked to actual gait and EF, while the AC condition engages neural systems linked to visual processing and imagery in general. We further predict that the neural systems engaged during our imagined gait protocol are strengthened following our imagined gait intervention.

3 STUDY DESIGN

Design: We propose a single-blind study of cognitively-healthy older adults randomized to a phone-based motor imagery or visual imagery (active control) intervention for 12 weeks (36 sessions)

Outcomes: The primary outcome is post-intervention change in gait speed during actual walking and walking while talking.

Secondary and tertiary outcomes include improvements in cognitive performance during Talking and Walking While Talking, changes in blood-oxygen-level dependent signal during Walking and Walking While Talking, improvement in executive function, and other mobility-related cognitive processes (speed of processing, memory and spatial navigation), and improved gait variability and other quantitative gait parameters during walking and walking while talking (see Clinicaltrials.gov-NCT02762604 for a comprehensive list).

Study population: 48 Bronx and Westchester county residents between 65 and 85 years old will be randomized into a phone-based motor imagery or visual imagery (control) intervention for 12 weeks (36 sessions)

Study location: Pre and post-intervention visits will be held at the Albert Einstein College of Medicine.

Approximate duration of enrollment period and follow-up: Potential recruits who meet eligibility criteria on the telephone are invited to baseline assessment and then randomized to motor imagery or visual imagery intervention. Baseline study assessments are limited to 180 minutes over 1 day to avoid fatigue. Telephone assessments are 15 minutes. Post-intervention assessments will be conducted within 4 weeks of the completion of the intervention.

We plan to enroll and randomize 48 participants over 36 months (1-2 per month). If necessary, we will ask for a no cost extension to allow for additional time to process and analyze the data, write manuscripts, and possibly apply for a follow-up grant.

Randomization and Blinding: We will include a number of methods to reduce bias.

- Selection bias will be reduced by concealing treatment allocation until the participant is entered into trial.
- Primary outcome is an objective endpoint (gait speed) and not subjective mobility complaints.
- Motor imagery and visual imagery interventions will be administered individually, and at non-overlapping times.
- Participants and study staff will be instructed not to disclose group assignment or details of interventions.
- Study staff that administers baseline and post-intervention assessments will be different from those that administer the phone-based motor imagery and visual imagery interventions.

4 SELECTION AND ENROLLMENT OF PARTICIPANTS

4.1 Inclusion Criteria

- Adults between 65 and 85 years and older, residing in the community.
- Able to speak English at a level sufficient to undergo study procedures.
- Plan to be in the area for the next 3 months.

4.2 Exclusion Criteria

- Presence of dementia (telephone-based memory impairment screen < 5 or AD-8 score > 1).
- Presence of gait disorder diagnosed by clinician (e.g. neuropathy).
- Any medical condition or chronic medication use (e.g. neuroleptics) that will compromise safety or affect cognitive functioning.
- Terminal illness with life expectancy <12 months.
- Progressive, degenerative neurologic disease (e.g. Parkinson's disease, ALS).
- Major psychiatric disorders such as Schizophrenia.
- Pacemaker or any permanent metal implants like hip prosthesis (other than tooth fillings) and claustrophobia.
- Participation in other intervention trial or observational studies during the intervention period.

4.3 Study Enrollment Procedures

Participants will be recruited from the Bronx and Westchester areas. A letter explaining our study will be sent and followed by a telephone call a few days later. Those expressing interest will be screened with the Telephone MIS (33) (sensitivity 85%, specificity 86%) and AD-8 (34, 35) (sensitivity 74%, specificity 86%).

Baseline visit: Eligible participants are invited for baseline assessments. Written consent and baseline assessments will occur in our research center. On arrival, potential participants will review study information and sign consent. Eligible subjects will be randomly assigned to an intervention group after completing baseline assessments.

All reasons for ineligibility and for non-participation will be documented in the database.

Following the completion of baseline assessments, participants will be randomly assigned to either the motor imagery or visual imagery interventions. Group assignment will be displayed to RAs from a generated list using sequential study numbers so that the assistant who enrolls the participants will be blinded to randomization assignment of the next participant until assigned.

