5.2 Handling of Study Interventions

Both interventions will be administered in doses of approximately 45 minutes (three 15-minute sessions) per week for 12 weeks without crossover at our facilities. Each intervention session will be supervised by Drs. [name] and/or [name].

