The research staff and investigators will be present during all testing. All questionnaire completion will be done at a slow enough pace so as not to tire individuals. If subjects express physical or mental tiredness or discomfort during any of the assessments or training procedures, the procedure will be terminated immediately. Drs. [name] and [name] will be available onsite or cell at all times to address any safety concerns or clinical issues during the interventions.

All abnormal findings from the clinical, mobility, neuroimaging, and neuropsychological assessments done on baseline, screening visits, and post-intervention visits will be documented and reviewed by the DSMB chair. Periodic audits from the Albert Einstein College of Medicine IRB ensure compliance with confidentiality guidelines and adverse events monitoring.

7.2 **Methods and Timing for Assessing, Recording, and Analyzing Safety Parameters**

Answering health questionnaires and mental state examinations involve minimal psychological, social, or other risks. We do not expect any serious adverse events during these non-invasive tests and training programs of attention and executive function. The motor imagery and visual imagery interventions involve mental but no physical effort by the participants. Some people are bothered by feelings of confinement (claustrophobia), and by the noise made during MRI. Participants will be asked to wear earplugs or earphones while in the MRI machine. They may not participate in this study if they have a pacemaker, an implanted defibrillator or certain other implanted electronic or metallic devices.

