7.6 Safety Monitoring

Prior to beginning data collection, [name] and the DSMB Chair will reconfirm that our site has appropriate safety measures in place. The DSMB will meet with the entire research team to review the study protocols. Particular attention will be paid to outcome definition, study design, procedures for recording and reporting adverse events, and informed consent procedures and documentation.

At the initial meeting, the DSMB may recommend modifications or clarification of the protocol, and it will formulate its operating procedures (e.g., meeting schedule, reports due dates for the study statistician, unblinding policy, and what interim data may be released to the investigators). At the initial meeting the plans for interim monitoring for efficacy and futility will be presented to the DSMB as an aid for monitoring the trial.

We will train competent staff to conduct the interventions and assessments, ensure they understand the nature of the interventions, and understand adverse event reporting requirements. Trained clinical assistants, who will monitor the subject for any adverse events, will perform all assessments. We do not expect any serious adverse events during these non-invasive interventions. The clinical assistant will stop the testing procedures if subjects feel stressed or get embarrassed by their performance, and relay the information immediately to [name] or [name]. At least one investigator will be present onsite during all testing and intervention sessions. In addition Drs. [name] and [name] will be available by cellular telephone at all times to address any safety concerns or clinical issues.

Please see the Safety Monitoring Guidelines for further details (DSMP).

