9.2.1. Treatment Assignment Procedures

Group assignment randomization will be generated by [name] using sequential study numbers so that the assistant who enrolls the participants will be blinded to randomization assignment of the next participant until assigned. [name] will not be involved with subject testing or interventions.

Given the nature of our interventions, double-blinding both subjects and testers will not be feasible. But we will include a number of methods (besides randomization) to reduce bias.

- Selection bias will be reduced by concealing treatment allocation until the subject is entered into trial.
- Primary outcome is an objective endpoint (gait speed) and not subjective mobility complaints.

- Motor imagery and visual imagery interventions will be done at non-overlapping times.
- Participants and study staff will be instructed not to disclose group assignment or details of interventions.

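### The plan does not ensure that the person running the post-intervention gait test is blind to arm

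*Combined protocol and SAP*

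**What the plan says.** **Blinding.** Section 3 describes a single-blind study without naming the blinded party. Section 9.2.1 says that "double-blinding both subjects and testers will not be feasible".

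**Release of the assignment.** Section 4.3: "Eligible subjects will be randomly assigned to an intervention group after completing baseline assessments". Then: "Group assignment will be displayed to RAs from a generated list using sequential study numbers", arranged so that "the assistant who enrolls the participants will be blinded to randomization assignment of the next participant until assigned".

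**Separation of staff.** The last bullet on bias in Section 3: "Study staff that administers baseline and post-intervention assessments will be different from those that administer the phone-based motor imagery and visual imagery interventions". Section 9.2.1 repeats most of that list but not this bullet.

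**Supervision and presence.** Section 5.2: "Each intervention session will be supervised by Drs" (the names that follow are removed in the public copy). Section 7.1: "The research staff and investigators will be present during all testing". Section 7.6: "At least one investigator will be present onsite during all testing and intervention sessions". Section 10.3.3 asks only for a member of the research team.

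**Imagery at the visits.** Section 2.1 (Study Rationale) has the gait or control imagery given at every study visit. Section 5.1 has the calls in both arms follow the protocol used at the visit. Section 6.1 lists an imagery protocol before and after the intervention.

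**Other safeguards.** Sections 3 and 9.2.1 tell participants and staff not to reveal the assignment, and rely on gait speed being an objective endpoint.

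**The concern.** Participants rehearse either walking or objects three times a week, so they know their task. The blinding that can still protect the primary outcome is that of the person who runs the post-intervention walks, and the plan never states it.

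The walkway records speed objectively. It does not control how the walk is introduced or how much the walker is encouraged, and walking speed depends on effort. A tester who knows the arm and expects motor imagery to help could shift the post-intervention speeds in one direction. No later analysis could separate that shift from a treatment effect.

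**Working it through.** The main check compares the passages. The plan gives no figure to reproduce.

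**Step 1: who may know the arm before the post-intervention walk (weeks 12–16 in Section 6.1), and does the Section 3 rule exclude them from assessing?**

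| Person | How the arm may be known | Excluded by the Section 3 rule? |
|---|---|---|
| RA who delivers the calls | Gives the arm-specific sessions (5.1) | Yes |
| RA shown the list | Display after baseline (4.3) | No, unless also a caller |
| Doctor who supervises sessions | Section 5.2 | Not mentioned |
| Staff giving imagery at a visit | Arm-specific task at each visit (2.1) | Not mentioned |

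The safeguard in Section 4.3 hides only the next assignment, and only until it is made. That is allocation concealment. It protects the baseline walk, which comes before randomisation, and does nothing for the later one.

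**Step 2: are these people the gait assessors?** The documents do not say. RAs take consent (6.2.1), a designated RA makes the calls (5.1), and trained clinical assistants perform all assessments (7.6, 10.3.3). Nothing says whether those assistants overlap with the RAs shown the list.

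**Step 3: task order.** Randomisation follows the baseline assessments, so arm-specific imagery at the first visit should come after the baseline walk. Nothing fixes the order at the second visit. Section 6.1 lists GAITRite just above the imagery protocol but does not present its rows as a running order.

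**Step 4: what a bias would do, for illustration only.** The documents give neither an SD of change nor a bias. Assume a bias of 3 cm/s in favour of one arm at the post-intervention test, an SD of change of 8 to 12 cm/s, 24 per arm (Précis), no true effect and a two-sided 5% level.

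- Simple two-arm comparison of change: standardised shift d = 3/SD, noncentrality = d × √(24/2) = 3.464d, 46 degrees of freedom, critical t = 2.013.
  - SD 12: d = 0.250, noncentrality 0.866, rejection probability 0.136.
  - SD 8: d = 0.375, noncentrality 1.299, rejection probability 0.246.
- Planned focus (Section 9.4.1): the interaction of time, trial type and arm. With two times and two trial types this compares, between arms, each person's (change in walking) − (change in walking while talking). A bias b in both gives b − b = 0. A simulation (24 per arm, assumed SD 10, 20,000 runs) rejected in 5.0%. Only the difference between the biases in the two conditions reaches this test.

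These calculations leave out the Bonferroni correction in Section 9.4.2, which would lower the nominal level.

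**The case against.** The strongest reply is that no passage makes anyone who knows the arm the post-intervention gait assessor. The staff shown the list could be the callers, and the assessors are described as clinical assistants. The names are removed, so the doctors who supervise and the investigators present at testing can be matched only by role. Being onsite for safety is not the same as running the walk. This stands. A reader might infer that the assessor is in fact unblinded, or that the other passages cancel the separation rule; the documents support neither.

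It can also be said that staff separation is not the only safeguard, because participants and staff are told not to reveal the assignment. That is correct and it helps. But it cannot mask someone who has already been shown the list, supervised the sessions or given the arm-specific task.

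The missing bullet in Section 9.2.1 is weak evidence by itself. A shorter list does not withdraw what Section 3 promises.

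Finally, the endpoint is instrumented. That protects the recording of speed, but not the instruction and encouragement before and during the walk.

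**Conclusion.** The point holds as a gap in the plan: followed as written, it does not guarantee that the post-intervention gait assessor is blind to arm. Actual unblinding is not shown.

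The size is unknown. A reader might infer that the false-positive rate of the primary analysis rises to about 14–25%. The documents do not support that. The figure rests on an assumed 3 cm/s bias and assumed SDs of 8 to 12 cm/s, and it belongs to a simple two-arm comparison of change. An equal bias in both walking conditions leaves the planned three-way interaction at its nominal level.

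The exposure still matters. The objective in Section 1.1 is an arm difference in gait speed improvement in each condition. Section 9.1.1 would also count an effect on walking-while-talking speed alone, and such readings do take in a common bias. The change is worth making before post-intervention testing, because it is cheap and the bias cannot be removed afterwards.

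**What to change.** 1. In Sections 3 and 9.2.1, state that the post-intervention gait assessor is blind to arm. Bar anyone who has seen the assignment, supervised calls or given arm-specific imagery from administering those walks.
2. In Sections 4.3 and 9.2.1, display the assignment only to intervention staff. Withhold the allocation field and the attendance log in REDCap from assessment staff.
3. At both visits, do the GAITRite walks before any arm-specific imagery, and have intervention staff give that imagery. Holding back the assignment until the visit has closed would not work, because Section 2.1 places the arm-specific task within the visit.
4. Carry the Section 3 separation bullet into Section 9.2.1.
5. Reconcile Sections 7.1, 7.6 and 10.3.3 on who is present, so that investigators stay available onsite for safety while those who supervise calls are out of the room for the post-intervention walks.

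**Cost:** wording, database user rights, and some scheduling of staff and task order within visits. Section 3 already plans separate teams for assessment and for the calls.

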5 STUDY INTERVENTIONS

5.1 Interventions, Administration, and Duration

During **gait imagery training**, participants will be trained to iW, imagine talking (iT: reciting alternate letters of the alphabet out loud) and iWWT. They will be instructed to close their eyes during imagery, use both visual and kinesthetic imagery, and pay equal attention to both tasks in the iWWT condition. Seated at a desk, they will then complete two trials of imagery training in 16-seconds blocks for approximately 15 minutes. Imagery instructions will be presented auditorily, and the beginning and the end of a block will be initiated with a tone. During the first trial,

instructions will be detailed (i.e. “Imagine Walking: At the start of the next tone, close your eyes and imagine or envision yourself walking on the mat. At the start of the following tone, stop, and wait for further instructions”), but during the second trial they will simply be prompted to begin at the start of the tone (e.g. “Imagine Walking”). Following each trial, participants will be asked to evaluate the quality of their visual and kinesthetic images on a scale from 1 (no image; no sensation) to 5 (image as clear as seeing; as intense as executing the action). During **visual imagery training**, participants will be trained to imagine a set of concrete objects (e.g. giraffe) from a standardized set of pictures (36) that have been normed for name agreement, image agreement and visual complexity. Again, they will be instructed to close their eyes during imagery and will complete two trials of imagery training in 16 second blocks for approximately 15 minutes. Imagery instructions will be presented auditorily and the beginning and the end of a block will be initiated with a tone. Following each trial participants will be asked to evaluate the quality of their visual and kinesthetic images on a validated scale from 1 to 5 (37, 38).

During the **imagined gait protocol (in MRI)**, imagery prompts (e.g. imagine walking) will be presented auditorily and volume will be adjusted to ensure instructions can be heard clearly in the presence of scanning noise. Imagery will occur in 16-second blocks (eyes closed). A tone will indicate the beginning and the end of a block, and each block will be repeated six times. Following the imagery task, participants will again be asked to evaluate the overall quality of their visual and kinesthetic images on a 1-5 scale. During the **visual imagery protocol (in MRI)**, imagery prompts (e.g. imagine a giraffe) will be presented auditorily and volume adjusted to ensure instructions could be heard clearly in the presence of scanning noise. Again, imagery will occur in 16-second blocks (eyes closed). A tone will indicate the beginning and the end of a block, and each block will be repeated six times.

During the **imagined gait intervention**, participants will be called by the experimenter three times a week and be asked to iW, iT and iWWT following the same protocol as during their study visit. They will also be asked to rate their visual and kinesthetic qualities of their images on a 1-5 scale (37, 38) following each trial. During the **active control intervention**, participants will be called three times a week by the experimenter and be asked to imagine concrete objects following the same protocol as during their study visit. Participants will be contacted over the phone on Monday, Wednesday and Friday mornings (before 12 noon), unless other times or days are preferred. Calls will be made to a landline (unless cellphone is the only option for a particular participant), and participants will be instructed to sit down comfortably, and turn down any distracting noise (e.g. music or TV). If a participant is unavailable at the scheduled time, we will try to reach them later in the day, but if we are still unsuccessful, we will skip that particular session and wait until the next scheduled session. Any unexpected distractions or missed sessions will be carefully recorded, and examined to inform the development of full-scale RCT.

Performance monitoring and dose: The imagined gait and active control interventions will be administered by a designated RA in our research center under controlled conditions to protect internal validity of the study and to ensure compliance with protocol. Participants will also be instructed to take a seat and turn down any distracting noise (such as the radio or TV) before beginning each session. Following each 15-minute session, the visual and kinesthetic qualities of the images will be tracked to ensure that participants are fully engaged during each session.

Tracking imagery performance in this manner will also be informative to assess dose response effects, which will help in the design of future studies.

Frequency and duration: We propose a 36 session phone-based motor imagery or active control intervention over 12 weeks. Our intervention is of longer duration and greater intensity than most prior studies. Each training session takes 15 minutes to complete. Total training time over 12 weeks is 540 minutes. We can track performance to assess dose response effects, which will help in the design of future studies.

